4.3. Medical History

A tabulation of the general medical history coded terms will be provided by body system class and by intervention arm.

4.4. Prior and Concomitant Medications

All medications will be coded using the World Health Organization-Drug Dictionary. Tabulations will include prior and concomitant medications which are defined as follows:

- (i) Prior medications are defined as medications with a start date occurring before the date of DB Day 1 regardless of when dosing of the medication ended.
- (ii) Concomitant medications are defined as medications received on or after DB Day 1, medication that was received before initial dosing and continued after initial dosing of the study interventions, or medication with missing stop date.

Medication that started before the DB Day 1 and continued afterwards will be summarized both as prior and, separately, as concomitant medication. All concomitant medications will be allocated to one or multiple analysis phases depending on their start date and end date and also taking into account the eCRF flag to indicate if it is taken before/after study start or still ongoing.

- (iii) Concomitant medications of interest include the following categories:

- Oral contraceptives (hormonal contraceptive or systemic use)
- Medications that impact immune system (e.g. corticosteroids, cyclosporin, interferon)
- Medications that can be subject to CYP3A4 induction or CYP3A4 inhibition

A frequency tabulation of prior medications, and concomitant medications will be shown by Anatomical Therapeutic Chemical (ATC) class level 2, level 4 and preferred terms by intervention arm. In addition, the concomitant medications and concomitant medications of interest will be summarized by analysis phase. A listing of prior medications, concomitant medications, and concomitant medications of interest, respectively, will be also provided.

4.5. Protocol Deviations

Only major protocol deviations will be summarized.

Major protocol deviations and violations will be based on clinical review, but not limited to, the following criteria: (1) entered but did not satisfy criteria, (2) received wrong treatment or incorrect dose, (3) received a disallowed concomitant treatment, (4) developed withdrawal criteria but not withdrawn, (5) other. Protocol deviations will be closely monitored during the execution of the study and the final set of protocol deviation criteria will be finalized before the primary analysis database lock.

All major protocol deviations will be tabulated by coded term by intervention arm for the ITT analysis set. A listing of the major protocol deviations will be also presented.

A subset of major protocol deviations that may affect the assessment of efficacy (see list in [Attachment 1](#)) will be identified and finalized prior to the primary database lock to define the Per-Protocol population ([Section 2.3](#)). The number and percentage of ITT participants who are included in the PP analysis set will be summarized by intervention arm, accompanied by number and percentage of ITT participants who are excluded from the PP analysis set with the incidence of the major protocol deviations.

4.6. Extent of Exposure

Extent of exposure to study treatments will be summarized and presented based on the safety analysis set. The total duration of exposure during the DB phase will be calculated by each study treatment (JNJ-3989/ corresponding placebo, JNJ-6379/ corresponding placebo, and NA) separately and summarized descriptively by intervention arm. The duration of treatment with NA will be summarized also for the follow up phase by intervention arm.

Because of the different route and frequency of treatment administration across the 3 agents (for JNJ-3989 one subcutaneous injection once every 4 weeks, and for JNJ-6379 and for NA once daily oral dosing) the total duration of exposure (weeks) will be calculated for each agent as follows:

- JNJ-3989/placebo: [Min ((Date of last injection+27 days), Date of trial disposition, cut-off date) – date of first injection + 1] / 7

- JNJ-6379/placebo: (Min (Date of the last JNJ-6379/placebo administration, Date of treatment disposition for JNJ-6379/placebo, Date of trial disposition, Date of cut-off)- first drug administration date + 1)/ 7
- NA: (Min (Date of the last NA administration in the given phase, Date of discontinuation from NA, Date of trial disposition, Date of cut-off) - first drug administration date in the given phase + 1)/ 7

Cut-off dates will be defined to match the prespecified timepoints for IDMC periodical data reviews, interim analysis and the primary analysis, respectively (see Section 3).

The number and percentage of participants who skipped any dose of JNJ-3989/placebo or JNJ-6379/placebo or NA will be summarized separately for each study treatment by intervention arm during the DB phase. Additionally, the number and percentage of participants who missed 2 or more JNJ-3989/placebo injections, or who missed more than 5 JNJ-6379/placebo doses within a four week period, or who missed more than 5 doses of NA within a four week period.

For NA treatment, the total duration of exposure will be calculated separately for the DB and FU phase. For FU, the total duration will add up the weeks from the start of FU for those participants who met the requirement to re-start NA treatment. Those participants who stopped NA treatment at Week 48 and never restarted NA treatment thereafter will be counted as having zero weeks of NA exposure during the FU phase.

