- f. Minimum criteria for the availability of documentation supporting the eligibility criteria are described in the Source Documents section in Attachment 3 of the Master Protocol PLATFORMPAHPB2001. Clinical status will be checked at screening and again before first dose of study intervention. If a participant's clinical status changes (including any available laboratory results or receipt of additional medical records) after screening but before the first dose of study intervention is given such that he or she no longer meets all eligibility criteria, then the participant should be excluded from participation in the study.
- g. Medical history also includes mode of HBV transmission, stage of liver fibrosis, and alcohol consumption. Historical HBV DNA, HBsAg, HBeAg, and ALT data, if available, will be recorded in the CRF and/or the source document. Available historical data on a previous HBV genotype assessment will also be collected in the CRF.
- h. Liver disease staging assessments will be performed based on Fibroscan or liver biopsy results, obtained within 6 months (in case of Fibroscan) or within 2 years (in case of liver biopsy) prior to screening or at the time of screening.
- i. Participants must have absence of signs of cirrhosis or portal hypertension (absence of nodules, smooth liver contour, normal portal vein, spleen size <12 cm) and absence of signs of HCC on an abdominal ultrasound performed within 6 months prior to screening or at the time of screening or clinically relevant renal abnormalities. In case of suspicious findings on conventional ultrasound the participant may still be eligible if HCC or clinically relevant renal abnormalities have been ruled out by a more specific imaging procedure (contrast enhanced ultrasound, CT or MRI).
- j. In between study visits, participants will take oral study intervention at home and they will bring their study intervention with them to each study visit. At study visits, the study intervention should be taken on site.
- k. NA will be dispensed at Week 48 for intake during the follow-up phase in case the participant cannot stop NA treatment at Week 48.
- l. Complete physical examination, including height (only at screening), body weight, skin examination, and other body systems.
- m. Vital signs include supine SBP, DBP, pulse rate, and body temperature.
- n. All ECGs will be read centrally. Only on Day 1, an ECG will be collected and assessed locally prior to dosing.

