1.2. Trial Design

This is a Phase 2b, multicenter, randomized, double-blind, placebo-controlled, 2-arm parallel-group study to evaluate the efficacy of 48-week study intervention with a JNJ-3989+JNJ-6379+NA regimen compared to NA treatment alone, assessed by HBsAg seroclearance at Week 72 (ie, 24 weeks after completion of all study interventions at Week 48) without restarting NA treatment in HBeAg-negative virologically suppressed CHB-infected

participants who received NA treatment for at least 2 years prior to screening. All participants will stop all study interventions including NAs at Week 48 and will be followed up until Week 96. After completing this study, participants may have the option to enroll into a long-term follow-up study.

A target of 120 HBeAg-negative virologically suppressed CHB-infected male and female participants, 18-65 years (inclusive) of age, who received NA treatment for at least 2 years prior to screening will be randomized in a 2:1 ratio to one of the following intervention arms:

- Arm 1 (N=80): 200 mg JNJ-3989 + 250 mg JNJ-6379 + NA
- Arm 2 (N=40): Placebo + Placebo + NA

NA treatment refers to entecavir (ETV), or tenofovir disoproxil fumarate (TDF), or tenofovir alafenamide (TAF).

The study will be conducted in the following phases:

- **Screening phase:** 4 weeks. If necessary, eg, for operational reasons, the screening phase may be extended up to a maximum of 6 weeks on a case-by-case basis and in agreement with the sponsor.
- **Double-blind study intervention phase:** from Day 1 (ie, baseline) up to Week 48. All participants who complete 48-week study intervention should stop all study interventions including NAs at Week 48.
- **Follow-up phase:** for 48 weeks after the end of investigational intervention.

An Independent Data Monitoring Committee (IDMC) was commissioned for this study to monitor and review data in an unblinded manner on a regular basis to ensure the continuing safety of the study participants. The committee will meet periodically to review unblinded data, as well as the efficacy and safety results from the interim analyses (IAs) at prespecified time points (see Section 3). A separate IDMC SAP describes details of the safety and efficacy analyses included in the IDMC periodical data reviews.

In addition, an independent Flare Expert Panel (iFLEP) was appointed for flares monitoring and adjudication. Details on the IDMC and iFLEP activities are described in their respective charter.

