2.1. Analysis Phases and Visit Windows

2.1.1. Analysis Phase

The analysis phases are defined in [Table 1](#) below.

Table 1: Analysis Phases Start and End Dates

Analysis phase	Start date	End date
Screening	The date of signing the informed consent	1 day before the first study agent intake
Double-blind Study intervention	Date of first study agent intake	Maximum [Date of last study treatment (JNJ-3989/placebo or JNJ-6379/placebo) intake, Week 48] + 5 days ^a or cut-off date ^b , whichever comes first

Table 1: Analysis Phases Start and End Dates

Analysis phase	Start date	End date
Follow-up	End of the double-blind study intervention phase + 1 day	The end date will be derived as trial termination date (date of last contact) or cut-off date ^b , whichever comes first

^a +5 days is only attributed to adverse events and concomitant medications.

^b Cut-off dates will be defined to match the prespecified timepoints for IDMC safety monitoring, interim analyses, the primary analysis and the final analysis, respectively.

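### SAP 4.6 gives two different start points for follow-up NA exposure, and selects participants by meeting restart criteria rather than by taking NA

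*SAP*

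**What the plan says.** SAP 4.6 (Extent of Exposure) summarizes NA duration by arm in the safety set and splits it by phase: "For NA treatment, the total duration of exposure will be calculated separately for the DB and FU phase". Three statements in the section then bear on follow-up.

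- **The formula.** Exposure ends at the earliest of the last NA dose in the phase, NA discontinuation, trial disposition or cut-off. The subtracted start date is the "first drug administration date in the given phase + 1)/ 7".
- **The follow-up sentence.** For follow-up, "the total duration will add up the weeks from the start of FU for those participants who met the requirement to re-start NA treatment".
- **The zero rule.** Participants who stopped NA at Week 48 and "never restarted NA treatment thereafter will be counted as having zero weeks of NA exposure during the FU phase".

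The surrounding design matters. Follow-up begins at "End of the double-blind study intervention phase + 1 day" (SAP 2.1.1). Under SAP 1.2, "All participants who complete 48-week study intervention should stop all study interventions including NAs at Week 48", so for most participants any follow-up NA comes after an untreated gap. The protocol also allows for participants who do not stop: a footnote to the treatment-phase Schedule of Activities states that "NA will be dispensed at Week 48 for intake during the follow-up phase in case the participant cannot stop NA treatment at Week 48".

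**The concern.** For a restarter, the start of follow-up and the first NA dose in follow-up are different dates, separated by the time spent off NA. The section uses both as the start of exposure and does not rank them. The closing sentence is the one written specifically for follow-up, so a programmer could reasonably let it override the general formula. Two programmers working from the same text could then produce materially different tables.

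The group is also mis-specified. The sentence covers those who satisfied the restart requirement, whereas exposure should depend on whether NA was taken. The SAP itself keeps these groups apart: section 5.3.1.1.8 identifies them from separate CRF pages, and 5.3.2.1.4 cross-tabulates one against the other.

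At stake is the by-arm description of how long NA was taken after the planned stop, which is useful background in a trial of finite treatment.

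**Working it through.** The SAP states no exposure figure, so there is nothing to reproduce. The check applies both rules to the same participant.

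**Inputs.** Follow-up Week 48 has target day 337 and Follow-up Week 24 (study Week 72) has target day 169 (SAP 2.1.3, Table 2). Restart days are assumptions placed at scheduled visits, with NA then taken without a break to the end date.

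**Rules, in weeks**, with L the last NA day and R the restart day:

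- Formula: (L − R + 1)/7
- Follow-up sentence read literally: (L − 1 + 1)/7 = L/7
- Difference: (R − 1)/7, which is the untreated gap

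**NA taken to follow-up Day 337** (literal value 337/7 = 48.1):

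| Restart | Formula | Literal | Excess | Ratio |
|---|---|---|---|---|
| Week 4 (Day 29) | 309/7 = 44.1 | 48.1 | 4.0 | 1.09 |
| Week 12 (Day 85) | 253/7 = 36.1 | 48.1 | 12.0 | 1.33 |
| Week 20 (Day 141) | 197/7 = 28.1 | 48.1 | 20.0 | 1.71 |
| Week 36 (Day 253) | 85/7 = 12.1 | 48.1 | 36.0 | 3.96 |

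Dropping the extra day gives 48 weeks against 44, 36, 28 and 12.

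**Cut at follow-up Day 169** (literal value 169/7 = 24.1): restarts on Days 57, 85 and 141 give 113/7 = 16.1, 85/7 = 12.1 and 29/7 = 4.1 weeks by the formula.

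**NA never stopped:** R = 1, so both rules give 48.1 weeks.

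**Who is covered by the follow-up text:**

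| Participant | Follow-up sentence | Zero rule | Formula |
|---|---|---|---|
| Met criteria, restarted | yes | no | applies |
| Met criteria, stopped at Week 48, never restarted | yes | yes | no dose to use |
| Restarted at the investigator's discretion, criteria not met | no | no | applies |
| Never stopped NA | not named | no | applies |
| Criteria not met, stopped and never restarted | no | yes | no dose to use |

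The second row can occur: SAP Attachment 1 lists deviations (numbers 17 to 20) for participants who met a restart criterion and did not start NA. The third can occur because Protocol 6.7 permits an earlier, discretionary restart. The fourth is provided for in Protocol 6.6.

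**The case against.** The strongest reply is that the formula is explicit, applies to each phase and already excludes the weeks before a restart. Adding up weeks from the start of follow-up can be read as summing the NA weeks that fall within follow-up, which agrees broadly with the formula. The zero rule points the same way, since it gives no credit for untreated time. The formula also handles discretionary restarters and those who never stopped, because both have a first and last NA date in follow-up. Someone who never restarted has an explicit zero.

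Much of this stands. A reader might infer that untreated weeks **will** be counted as exposure. The documents do not support that: it happens only if the follow-up sentence overrides the formula and is taken literally, and the zero rule suggests it was not intended. A reader might also infer that every restarter's figure is inflated by more than 10%, but a Week 4 restart gives 1.09.

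The reply does not remove the defect. The benign reading has to be supplied by the reader, the section does not rank its rules, and the selection by criteria met is wrong on either reading.

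**Conclusion.** SAP 4.6 is internally inconsistent on follow-up NA exposure, in both its start point and its group. If the follow-up sentence were applied literally, each restarter's exposure would be overstated by the length of the untreated gap: 4 weeks for a Week 4 restart and 36 weeks for a Week 36 restart, given uninterrupted NA to Follow-up Week 48. If the formula governs, the overstatement is nil.

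These are per-participant figures for assumed restart weeks. The effect on an arm's summary depends on how many participants restart and when. Neither is given, and participants with zero weeks or with NA never stopped contribute no start-point discrepancy.

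A reader might go on to infer that the arms would be distorted unequally because the regimen delays relapse. The documents do not show this. The relapse-timing evidence in Protocol 2.1 compares TDF with ETV, and NA type is a randomization stratification factor.

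The consequence is confined to a descriptive safety-set table. The re-treatment endpoint is a proportion meeting criteria, and the primary estimand uses re-treatment as an event, so neither draws on exposure weeks. The primary endpoint, alpha and power are unaffected. The point is small but clear, and worth correcting because the correction costs almost nothing.

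**What to change.** Replace the follow-up sentence and the zero-week sentence after it in SAP 4.6 with one rule:

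> For FU, NA exposure is calculated for all participants who took NA during follow-up, whether or not the re-treatment criteria were met. It runs from the first NA administration in FU (FU Day 1 if NA was not stopped) to the earliest of the last NA administration in FU, discontinuation of NA in FU, trial disposition and cut-off. All other participants count as zero weeks.

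This keeps the first-to-last-dose span of the existing formula. If the sponsor prefers to sum separate NA intervals, so that interruptions after a restart are left out, the follow-up part of the formula must change in the same way. Otherwise anyone with an interrupted restart would again fall under two rules.

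The cost is a short text edit and a check of the exposure derivation. No new data are needed: NA administration is already recorded in the CRF, and SAP 5.3.1.1.8 already uses that page to identify actual restarters.

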4.7. Treatment Compliance

Treatment compliance will be summarized for the safety analysis set by intervention arm for each study treatment except NA.

Treatment compliance (%) is defined as follows:

For JNJ-3989/placebo: (Total number of injections received/ 12) * 100%

For JNJ-6379/placebo: (Total medication intake / 4 *7 *48) * 100%

As the 250 mg daily dose of JNJ-6379/placebo consists of 4 tablets (2 tablets of 100 mg strength and 2 tablets of 25 mg strength), the denominator is 1,344 tablets= 4*7*48. The numerator representing the total medication intake for JNJ-6379/placebo is calculated as:

Total medication intake = (Total number of tablets dispensed–Total number of tablets returned)

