7. DISCONTINUATION OF STUDY INTERVENTION AND PARTICIPANT DISCONTINUATION/WITHDRAWAL

If a participant discontinues study intervention for any reason before Week 48, the participant will have an early withdrawal visit and will enter follow-up unless he/she withdraws consent. If the reason for withdrawal from the study is withdrawal of consent, then the participant will be offered an optional safety follow-up visit. Study intervention assigned to the participant who discontinued study intervention may not be assigned to another participant.

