2.3. Analysis Sets

All randomized analysis set: All participants who were randomized in the study. Participants will be analyzed according to the study intervention they were randomly assigned to.

Intent-to-Treat analysis set (ITT): All participants who were randomized in the study and received at least one dose of study treatment within this ISA. Participants will be analyzed according to the study intervention they were randomly assigned to.

Modified Intent-to-Treat analysis set (mITT): All participants who were randomized in the study and received at least one dose of study treatment excluding those participants impacted by the pandemic defined as those participants who, because of COVID-19 or similar pandemics related reasons, withdrew prematurely from the study prior to Week 72, or had no efficacy assessment for

the primary endpoint. COVID-19 or similar pandemics related reasons may include for example missed visits due to travel restriction, shortage of lab kits at the planned visit, missed collection of blood sample at key time points for the primary efficacy endpoint, etc. Participants will be analyzed according to the study intervention they were randomly assigned to.

Safety analysis set: All participants who received at least one dose of study treatment within this ISA. Participants will be analyzed according to the study intervention they actually received.

Per protocol analysis set (PP): All participants in the ITT analysis set who do **not** have any of the selected major protocol deviations that may affect the assessment of efficacy in terms of the primary endpoint at Week 72. The selected major protocol deviations for efficacy analysis purposes that will be used to identify the participants included in the PP set are described in Section 4.5 and [Attachment 1](#). Participants will be analyzed according to the study intervention they were randomly assigned to.

The PK analysis set: All participants who have received at least one dose of study treatment and have at least one valid blood sample drawn for PK analysis.

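### SAP 4.7 divides doses taken by the full 48-week plan for everyone, so the compliance percentage mixes adherence with early discontinuation

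*SAP*

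**What the plan says.** SAP 4.7 gives one formula per agent.

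- **JNJ-3989/placebo:** "For JNJ-3989/placebo: (Total number of injections received/ 12) * 100", expressed as a percentage.
- **JNJ-6379/placebo:** intake over a fixed tablet count. "As the 250 mg daily dose of JNJ-6379/placebo consists of 4 tablets", and so "the denominator is 1,344 tablets= 4*7*48". The numerator comes from drug accountability: "Total medication intake = (Total number of tablets dispensed–Total number of tablets returned".

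On scope, "Treatment compliance will be summarized for the safety analysis set by intervention arm for each study treatment except NA". SAP 2.3 defines that set broadly: "Safety analysis set: All participants who received at least one dose of study treatment within this ISA". Early discontinuers are therefore included and measured against the same constants as completers.

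The protocol expects some participants to stop early. Section 7 states: "If a participant discontinues study intervention for any reason before Week 48, the participant will have an early withdrawal visit and will enter follow-up". Section 7.1 lists situations in which both agents (or placebos) must be stopped before Week 48, among them severe rash or allergic reaction, eGFR, QTcF, virologic breakthrough and ALT/AST criteria.

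Neither document gives any other compliance percentage.

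**The concern.** A compliance percentage is normally read as doses taken out of doses due. Protocol 6.4 leans the same way, treating poor compliance as intake that departs from the protocol. A participant stopped under Protocol 7.1 has followed the protocol, and no further doses are due, yet SAP 4.7 leaves the rest of the 48 weeks in the denominator.

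Elsewhere the SAP keeps the two ideas apart. Discontinuation before Week 48 is its own intercurrent event in SAP 5.2.2. The exposure formulas in SAP 4.6 end at participant-specific dates.

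At stake is how the table is read. A low value could mean poor adherence on treatment or a protocol-required stop, and the percentage cannot tell them apart. An imbalance in discontinuation would appear as an imbalance in compliance even if adherence were identical.

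**Working it through.** **Inputs.** Four tablets per day, the 12-injection and 1,344-tablet denominators (SAP 4.7); JNJ-3989 every 4 weeks (Protocol 6.1); visit days 85, 169 and 253 for Weeks 12, 24 and 36 (Protocol 1.3.1).

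**Reproducing the plan's figures.** 4 × 7 × 48 = 1,344 tablets. Injections at Weeks 0, 4, …, 44 number 12. Both agree with SAP 4.7.

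**One participant, no missed dose.** Tablets = 4 × stop day / 1,344. Injections = number given / 12, shown with and without an injection at the stop visit.

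| Last day | Tablets | Tablet % | Injections, stop visit given | Injections, stop visit not given |
|---|---|---|---|---|
| 85 | 340 | 25.3% | 4/12 = 33% | 3/12 = 25% |
| 169 | 676 | 50.3% | 7/12 = 58% | 6/12 = 50% |
| 253 | 1,012 | 75.3% | 10/12 = 83% | 9/12 = 75% |

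For comparison, a completer who misses half of all tablets scores 672/1,344 = 50%, practically the same as a perfectly adherent participant who stops at Day 169.

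**Arm means.** The documents give no discontinuation rates, so the rates below are assumptions. Everyone is fully adherent while on treatment, and a fraction d stops at Day 169. Mean tablet compliance = 100 × [1 − d × (1 − 0.503)].

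- d = 10% v 2.5%: 100 × (1 − 0.10 × 0.497) = 95.0% v 100 × (1 − 0.025 × 0.497) = 98.8%, a gap of 3.7 points before rounding.
- d = 15% v 5%: 92.5% v 97.5%, a gap of 5.0 points.

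For a stop at week w the gap is approximately 100 × (d1 − d2) × (1 − w/48) points:

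| Discontinued | Week 12 | Week 24 | Week 36 |
|---|---|---|---|
| 10% v 5% | 3.75 | 2.5 | 1.25 |
| 20% v 5% | 11.25 | 7.5 | 3.75 |

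**With an on-treatment denominator.** At Day 169, tablets read 676/(4 × 169) = 100% and injections 7/7 or 6/6 = 100%. Under the same assumptions the gap between arms is zero.

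**The case against.** The case for leaving SAP 4.7 alone has several parts.

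- **The ratio is explicit and recognisable.** Dose received as a share of a fixed regimen is a legitimate quantity, and it suits a trial in which stopping before Week 48 counts as non-response. This stands, but as an argument for a different label: under the name *compliance* the ratio will be read as adherence.
- **Other tables carry much of the information.** SAP 4.1 reports treatment discontinuation and reasons. SAP 4.6 reports exposure duration, participants who skipped any dose, and those who missed 2 or more injections or more than 5 JNJ-6379 doses in four weeks. This stands and limits the harm. Those tables let a reader see early stopping and dosing gaps, but none gives the percentage of scheduled doses taken while on treatment.
- **The between-arm gap is hypothetical.** This also stands. The first example needs 8 of 80 v 1 of 40 participants to stop at Week 24, and the median would still be about 100% in both arms.
- **An on-treatment ratio has its own blind spot.** A participant who simply chooses to quit can score 100%, and the result depends on how the stop date is recorded. Temporary interruptions allowed by the COVID-19 appendix would remain in the denominator. The fix must therefore define the end date and be read beside the disposition table.

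A reader might infer that early stoppers are classed as non-compliant. They are not: SAP 4.7 sets no threshold or category and only produces a percentage. A reader might also infer that the percentage decides who enters the per-protocol set or counts as a non-responder. It does not: both rest on other rules, with the relevant deviations listed in Attachment 1.

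**Conclusion.** The denominator is wrong for a quantity called compliance, and the point is minor. It follows directly from SAP 4.7 that a participant who takes every dose and stops early is shown with a low percentage, about 25%, 50% or 75% of tablets at Day 85, 169 or 253. This needs no assumption beyond full adherence up to the stop.

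The arm-level figures (95.0% v 98.8%, or 92.5% v 97.5%) do rest on assumed discontinuation rates and a common stop at Week 24. They illustrate the mechanism. They do not predict that Arm 1 will look worse, because the documents do not say which arm will have more discontinuations.

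No hypothesis test, estimand or analysis set uses the percentage. The consequence is one descriptive table that could be misread.

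**What to change.** Redefine compliance in SAP 4.7 over each participant's own treatment period, capped at Week 48:

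- **JNJ-3989/placebo:** injections received / injections scheduled before the recorded treatment-disposition date. An injection given on that date counts in both numerator and denominator.
- **JNJ-6379/placebo:** tablets taken / (4 × days from first dose to the JNJ-6379/placebo treatment-disposition date).

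State that the end date is the date of the decision to stop, and apply it the same way to both agents and both arms. If the 48-week ratio is also wanted, keep it under the label *percentage of planned 48-week dose received*.

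In the same edit, bracket the displayed JNJ-6379 formula as / (4*7*48). Evaluated left to right as printed, it does not divide by 1,344, although the following sentence makes the intention clear.

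The cost is a few lines of SAP text and one denominator per agent in the code. No new data are needed: SAP 4.1 already reports treatment disposition by treatment and lists discontinuation dates, and SAP 4.6 already uses the JNJ-6379 disposition date. The small downside is that the new ratio does not show voluntary early stopping, so a footnote should direct readers to the disposition and exposure tables of SAP 4.1 and 4.6.
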